**Description:**

- The purpose of this reporting and analysis plan (RAP) is to describe the final planned analyses and output to be included in the Clinical Study Report for Protocol 200722.
- This RAP is intended to describe the planned safety analyses required for the study.
- This document will be provided to the study team members to convey the content of the final Statistical Analysis Complete (SAC) Deliverable.
- Change in Version 2.0: Change from '<70' to '<4' for cognitive scale score, gross motor scale score and fine motor scale score of >2 SDs below mean score in Section 2.2.

## 1. REPORTING & ANALYSIS PLAN SYNOPSIS

Overview	Key Elements of the RAP
Purpose	
 
• This Reporting and Analysis Plan (RAP) details all planned safety analyses and outputs required for the final Clinical Study Report (CSR) of study 200722.
 

Protocol	
 
• This RAP is based on the original protocol (Dated: 14-May-2014), protocol amendment 01 (Dated: 17-Aug-2015), protocol amendment 02 (Dated: 01-Nov-2018) of study GSK200722 [GlaxoSmithKline Document Numbers: 2014N194466_00, GlaxoSmithKline Document Numbers 2014N194466_01, and GlaxoSmithKline Document Numbers 2014N194466_02] and the most recent version of the electronic Case Report Form (eCRF).
 

Objective	To assess the safety and outcomes in infants and children who were exposed to retosiban or comparator in the Phase III Spontaneous Preterm Labor (SPTL) treatment studies.
Endpoint	
Morbidity and mortality endpoints.
 
Neurodevelopment endpoints.
 
Exploratory resource utilization endpoint.
 
Details are further defined in Section 2.2.

Study Design	Long-term infant and child follow-up study (with no medical interventions or study visits to an investigational site required), during which parents or legal guardians will complete developmental questionnaires and other data on their children's health status via an electronic device at prespecified intervals until their children reach 24 months corrected age (or chronological age, if applicable), to prospectively assess safety and outcomes of all infants and children born to women who received at least 1 dose of retosiban or comparator in any of the Phase III SPTL treatment studies.
Planned Analyses	
 
• There is no formal interim analysis planned for this study.
 
• Final safety analyses are detailed within Section 3.2.
 
• All decisions regarding final analyses, as defined in this RAP document, will be made prior to Database Freeze (unblinding) of the study data.
 

Analysis Population	
 
• The primary population for safety assessment will be the Infant Safety population.
 
• The ARIOS Safety population is a subset of the Infant Safety population for which the mother/infant pairs who enrolled into the ARIOS study
 

Hypothesis	
 
• The objective of the study is to describe the safety and morbidity and mortality outcomes of children exposed to treatment during Phase III SPTL studies investigating retosiban or comparator for the treatment of SPTL.
 
• No type I error adjustments are planned.
 

Safety Analyses	

Descriptive statistics will be used to describe the safety and morbidity and mortality outcomes of children exposed to treatment during the Phase III SPTL studies investigating retosiban or comparator for the treatment of SPTL.

Descriptive statistics will be used to describe the clinical safety in terms of neurodevelopment in infants and children exposed to retosiban or comparator.

Serious Adverse Events (AEs) will be summarized by in infants exposed to retosiban or comparator in the Phase III SPTL treatment studies.

-----------------	--

## 2. SUMMARY OF KEY PROTOCOL INFORMATION

### 2.1. Changes to the Protocol Defined Statistical Analysis Plan

Due to early termination of the study, not all originally planned data analyses as outlined in the protocol will be performed. More details are given in Section 8.

### 2.2. Study Objective(s) and Endpoint(s)

Objectives	Endpoints

To characterize the clinical safety in terms of infant and child morbidity and mortality in infants and children exposed to retosiban or comparator in utero

	

Proportion of infants and children with newly diagnosed (after 28 days post EDD) chronic medical conditions by type of condition will be recorded and include the following:

Respiratory conditions

Chronic lung disease

Reactive airway disease

Vocal cord paralysis

Airway obstruction

Neurological conditions

Cerebral palsy

Seizure disorder

Hydrocephalus requiring shunt

Sensory conditions

Vision

Vision impairment

Blindness in 1 or both eyes, or sees light only

Hearing

Hearing impairment

Deafness in 1 or both ears

Hearing impaired, uncorrected even with aids

Gastrointestinal conditions

GERD (moderate to severe)

Tube/parenteral feeding

Short bowel syndrome

Cardiovascular conditions

Pulmonary hypertension

Hypertension

Renal conditions

Renal impairment requiring dialysis

Growth parameters

Poor weight gain

Reduced length

Reduced head circumference

Failure to thrive

Proportion of infants and children with newly diagnosed (after 28 days post EDD) congenital anomalies

Proportion of infant and child deaths that occur after 28 days post EDD and until 24 months chronological age

Objectives	Endpoints
	
 
• Neurodevelopment endpoints assessed at ages 9, 18, and 24 months, corrected for prematurity: 
 
• Proportion of infants with an ASQ-3 score in the black zone in any domain
 
• Proportion of infants with an ASQ-3 score in the black zone for gross motor skills
 
• Proportion of infants with an ASQ-3 score in the black zone for fine motor skills
 
• Proportion of infants with an ASQ-3 score in the black zone for communication
 
• Proportion of infants with an ASQ-3 score in the black zone for problem-solving
 
• Proportion of infants with an ASQ-3 score in the black zone for personal-social skills
 
• Proportion of infants referred for developmental evaluation (using BSID-III)
 
• Proportion of infants with a BSID-III score <math>>2</math> SDs below the mean score for the cognitive scale (<math><4</math>)
 
• Proportion of infants with BSID-III score <math>>2</math> SDs below the mean score for the gross motor scale (<math><4</math>)
 
• Proportion of infants with BSID-III score <math>>2</math> SDs below the mean score for the fine motor scale (<math><4</math>)
 
• Proportion of infants with a BSID-III score <math>>2</math> SDs below the mean score for the language scale (<math><70</math>)
 
• Proportion of infants with a CBCL/1.5-5 score above the 97th percentile for a subset of prespecified questions that relate to attention and hyperactivity problems
 
• Proportion of infants indicated as needing further evaluation after completion of the M-CHAT-R/F
 
• Proportion of infants referred for neurological evaluation to determine diagnosis of cerebral palsy
 
 
 
• Proportion of infants with at least 1 of the following indicators of neurodevelopmental impairment: 
 
• Hearing impaired, uncorrected even with aids (at 24 months chronological age)
 
• Blindness in 1 or both eyes, or sees light only (at 24 months chronological age)
 
• Cerebral palsy (moderate and severe) (at 24 months corrected age)
 
• Cognitive impairment: BSID-III Cognitive Scale Score of <math>>2</math> SDs below mean score (<math><4</math>) (at 24 months corrected age)
 
• Motor impairment: BSID-III Motor Composite Scale Score of <math>>2</math> SDs below mean score (<math><70</math>) (at 24 months corrected age)
 
• Diagnosis of ASD, ADD, or ADHD
 
 
 


Objectives	Endpoints
Exploratory 
 
To characterize parental productivity loss related to a sick child and infant resource utilization in terms of hospital admissions, length of stay, ER/UC visits, surgical procedures, and referral to specialty care or therapy visits for infants (up to age 2 years) exposed to retosiban or comparator in utero
 
	
 
Number of hospital admissions, proportion of infants and children with any hospital admission, post-birth hospitalization discharge, by principal and secondary discharge diagnosis, type of hospital unit admitted to (e.g., NICU, Pediatric, PICU, Nursery level 3, ICU), and length of hospital stay per unit after 28 days post EDD and until 24 months chronological age
 
Combined length of hospital stay in days for all hospital admissions (for infants discharged from the delivery hospitalization and for babies who were never discharged home post-delivery) after 28 days post EDD and until 24 months chronological age Number of surgical procedures (details of type and whether performed on an inpatient basis or at an outpatient/surgical center will be collected up to 24 months chronological age only) after 28 days post EDD and until 24 months chronological age Number of ER/UC visits and proportion of infants with any ER/UC visit after 28 days post EDD and up to 24 months chronological age
 
Number of specialty care or therapy visits and proportion of infants referred for specialty care or therapy by type of care/therapy after 28 days post EDD and up to 24 months chronological age
 
Parental productivity loss related to infant hospital admissions, ER/UC visits, or specialist care after 28 days post EDD and up to 24 months chronological age
 

ADD = attention deficit disorder; ADHD = attention deficit hyperactivity disorder; ASD = autism spectrum disorder;

ASQ-3 = Ages and Stages Questionnaire-3; BSID-III = Bayley Scales of Infant Development, third edition;

CBCL/1.5-5 = Child Behavior Checklist for Ages 1.5 to 5; EDD = estimated date of delivery; ER/UC = emergency

room/urgent care; GERD = gastroesophageal reflux disease; ICU = intensive care unit; M-CHAT-R/F = Modified

[figure not shown]
Checklist for Autism in Toddlers-Revised with Follow-Up; NICU = neonatal intensive care unit; PICU = pediatric

intensive care unit.

 Chronological age is age [in months] after the infant was born

 Corrected age is age [in months] after expected date of full-term delivery (chronological age minus the number of months that the infant was born early)

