4.4. Withdrawal Criteria

A child may be withdrawn from the study due to loss to follow-up or if the child's parent/legal guardian voluntarily withdraws consent. All data collected up to the time of withdrawal will be included in the analysis. If a parent/legal guardian fails to complete an assessment, but wishes to remain in the study, they will be allowed to continue by completing future assessments.

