7.1.2. Loss to Follow-Up

Children for whom follow-up information is never obtained will be considered lost to follow-up. These cases will be tallied in the applicable sections of the study reports. All other cases with some follow-up data will be analyzed up to the length of child follow-up.

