### **7.2.5. Neurodevelopment Impairment at the End of Study**

Number of infants and percentage of neurodevelopment impairment endpoints and individual components will be summarized at the end of study (24 months). Individual components at the end of study are listed in Section 2.2.

Motor composite score will be derived from fine motor and gross motor scaled scores in a similar fashion to language composite score described in Section 7.2.3

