### 10.6.2. Handling of Missing Data

Element	Reporting Detail
General	

• Missing data occurs when any requested data is not provided, leading to blank fields on the collection instrument :

[1] These data will be indicated by the use of a “blank” in subject listing displays.

[2] Answers such as “Not applicable” and “Not evaluable” are not considered to be missing data and should be displayed as such.

• For disposition and demographic data, no imputation will be done.

• For safety and neurodevelopment data, it will be assumed that the events of interest did not occur.

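### Read literally, the SAP scores a child with an earlier confirmed impairment but no 24-month assessment as unimpaired, and no rule says that the earlier diagnosis counts

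*SAP*

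**What the plan says.** SAP 2.2 lists six indicators, any one of which makes a child positive on the composite. Three are conditions that can be diagnosed at any time during follow-up, and each carries an age:

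- The hearing item is dated by chronological age: "Hearing impaired, uncorrected even with aids (at 24 months chronological age".
- The vision item uses the same age scale: "Blindness in 1 or both eyes, or sees light only (at 24 months chronological age".
- The cerebral palsy item adds a severity condition and switches to corrected age: "Cerebral palsy (moderate and severe) (at 24 months corrected age".

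The last item in the same list, "Diagnosis of ASD, ADD, or ADHD", carries no age. The ages come from Protocol 6.2.6 and Table 1; the SAP repeats them.

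SAP 7.2.5 sets the reporting point: "Number of infants and percentage of neurodevelopment impairment endpoints and individual components will be summarized at the end of study (24 months". SAP 10.6.2 sets the rule for missing values: "For safety and neurodevelopment data, it will be assumed that the events of interest did not occur". SAP 7.2 shows as N the whole treatment group, not the children assessed.

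Other sections point to using everything observed. SAP 4 puts data through the 2-year assessment into the summaries. Protocol 4.4 says "All data collected up to the time of withdrawal will be included in the analysis", and Protocol 7.1.2 says "All other cases with some follow-up data will be analyzed up to the length of child follow-up".

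**The concern.** Blindness, uncorrected hearing loss and cerebral palsy are asked about from the first Child Health Inventory at 2 months and at each later one (Protocol 6.2.1 and 6.2.1.1). The protocol's section on confirming parent-reported data requires medical confirmation of these endpoints, and it sends a reported worsening or resolution back to the provider. A child may therefore have a confirmed diagnosis on file well before 24 months.

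If that child then leaves or misses the last assessment, the age label, the 24-month reporting point and the missing-data assumption together give a negative score. This differs from the usual missing-outcome problem, because here the outcome has been observed. Restricting the table to children assessed at 24 months would not help, since the known case would still drop out.

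Protocol 6.2.6 makes this composite the overall measure of neurodevelopmental impairment in a safety study, and Protocol 3.2 itself warns that loss to follow-up can introduce ascertainment bias. A rule that can remove known cases and never known non-cases errs toward reassurance.

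**Working it through.** The plan gives no event rate, 24-month missing rate or target figure for this endpoint, so there is no figure to reproduce. The check is a comparison of texts plus the weight of one child.

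**1. Trace one child through the rules.** Suppose that blindness is reported at the 12-month inventory and confirmed by the provider, and that the child is lost after 15 months.

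- SAP 2.2 asks for blindness at 24 months chronological age. There is no 24-month record.
- SAP 7.2.5 summarizes at 24 months. The field is blank.
- SAP 10.6.2 treats the blank as no event. The child counts as negative in Table 10.9 (Infant Safety) and Table 20.9 (ARIOS Safety) and stays in N.
- SAP 4 and Protocol 4.4 and 7.1.2 would bring the 12-month finding into the analysis. None says how an endpoint labelled with a later age should use it.

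Two programmers could follow the text and produce different tables.

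**2. Which components are affected.**

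- *Blindness and uncorrected hearing loss:* the chronic-condition categories in SAP 2.2 match the composite categories, so the earlier positive is already in the data.
- *Cerebral palsy:* Protocol 6.2.6 requires moderate or severe disease, GMFCS grade 2 to 5. An earlier diagnosis is a composite positive only if it was graded so. Protocol Table 2 (footnote 8) and 6.2.5.1 make the 24-month referral only for children without an existing diagnosis, so a child already diagnosed gets no new referral by design.

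**3. Weight of one lost case.** Enrolled numbers are in Protocol Appendix 1 (Amendment 02 justification): 49 + 43 + 6 = 98. The documents do not state the Infant Safety N. I assume the parent-trial group sizes in Protocol 1.1.1: retosiban 10 + 50 = 60, atosiban 47, placebo 13. The change per child is 100/N.

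| Group | ARIOS Safety | Infant Safety (assumed N) |
|---|---|---|
| Retosiban | 100/49 = 2.0 points | 100/60 = 1.7 points |
| Atosiban | 100/43 = 2.3 points | 100/47 = 2.1 points |
| Placebo | 100/6 = 16.7 points | 100/13 = 7.7 points |
| All comparators | 100/49 = 2.0 points | 100/60 = 1.7 points |

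These changes reach the composite only if the child has no other qualifying indicator. Otherwise only the component row changes.

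**4. Illustration, with assumed inputs.** Let p be the share of children with an earlier confirmed, unresolved diagnosis of this kind, and d the share of those without a 24-month assessment. The literal rule reports p(1 − d). With p = 10%:

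- d = 10%: 9%
- d = 20%: 8%
- d = 30%: 7%
- d = 40%: 6%

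The chance of losing at least one case among 49 retosiban infants is 1 − (1 − pd)^49. It is 0.22 at p = 5%, d = 10% and 0.95 at p = 15%, d = 40%. Neither p nor d is in the documents, so this shows sensitivity and is not an estimate.

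**The case against.** The best defense is that the SAP is silent on this point and not wrong. A label of 24 months can be read as the child's status at that age, whichever form supplied the evidence. SAP 10.6.2 describes missing data as blank fields, and a confirmed diagnosis is a recorded event. The inventory is cumulative: later rounds ask whether a reported condition is worse, better or resolved. SAP 3 leaves derivations to an ADaM specification and SAP 10.8 leaves layouts to a shells document. Neither is available here, and either may already carry diagnoses forward.

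That reading is plausible, and it limits the point. A reader might infer that the plan deliberately ignores earlier diagnoses. The documents do not support that, because no sentence says so. But no sentence makes the cumulative reading prevail over 10.6.2 either, and the stated rules applied as written give the wrong score.

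Four further objections stand in part:

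- **The case is not lost from the report.** The same diagnosis is counted in Tables 10.6 and 20.6 and, for enrolled children, shown in Listing 39. The effect is confined to Tables 10.9 and 20.9.
- **Cerebral palsy is weaker ground.** The referral rule suggests that an earlier diagnosis is meant to stand, and no section requires a GMFCS grade when an earlier report is confirmed.
- **The ages are the protocol's own.** A change in the SAP should be presented as clarifying Protocol 6.2.6.
- **The size is unknown.** It is tempting to carry a relative loss of 10% to 30% over to the whole composite. That range would be an assumption, and it would apply to three of six components, since an affected child may qualify through another indicator.

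**Conclusion.** The point holds as a conflict between stated rules. It is clear for blindness and uncorrected hearing loss, and it holds for cerebral palsy only where the earlier diagnosis was graded moderate or severe. The direction is certain under the literal reading: the composite can fall and cannot rise. The size is known only per child, as tabulated above. The large placebo figure mainly reflects a group of six.

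The conclusion assumes that at least one child has an earlier confirmed, unresolved diagnosis and no 24-month assessment, and that the unseen specification does not already settle the matter. The study is descriptive, so no test or error rate is affected. With groups this small, however, one child visibly changes the table, and the repair uses data already collected. It should be made before database freeze.

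**What to change.** 1. In SAP 2.2 and 7.2.5, count the hearing and vision components, and cerebral palsy graded moderate or severe (GMFCS 2 to 5), as present if medically confirmed at any time up to and including the 24-month assessment and not medically confirmed as resolved.
2. In SAP 10.6.2, state that the assumption of no event does not override an earlier confirmed positive.
3. Record this as a clarification of Protocol 6.2.6, and carry the same rule into the ADaM specification.
4. Footnote Tables 10.9 and 20.9 with the number of cases per group that rest on a confirmation before 24 months.

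The cost is a few sentences and one derivation, with no new data collection. The downside is small: a condition that resolved after the last contact would still be counted. The footnote shows the most cases that this could affect.

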## 2.3. Study Design

EDD = estimated date of delivery; HCP = health care provider; RCC = research coordinating center; RCC-PI = research coordinating center-principal investigator; SPTL = spontaneous preterm labor.

### Overview of Key Study Design Features

Design Features:	
 
Long-term infant and child follow-up study (up to 24 months corrected age (or chronological age, if applicable))
 
Subjects are infants and children born to women who received at least 1 dose of retosiban or comparator in any of the Phase III SPTL treatment studies.
 
This study does not require medical interventions or study visits to an investigational site.
 
Parents or legal guardians will be prompted at certain time points to complete developmental questionnaires and other data on their children's health status via an electronic device until infants and children have reached 24 months corrected age (or chronological age, if applicable).
 

Dosing:	
 
Infants and children enrolled in this study will not be administered any investigational product.
 

Treatment Assignment:	
 
The Phase III SPTL treatment study treatment group and strata to which mothers were dosed will be maintained during analysis of data from the child follow-up study.
 

Interim Analysis	
 
There is no formal interim analysis planned for this study.
 

## **2.4. Statistical Hypotheses**

The objective of the study is to describe the safety and morbidity and mortality outcomes of children exposed to treatment during Phase III SPTL studies investigating retosiban or comparator for the treatment of SPTL. These mortality and morbidity endpoints (as described in protocol Section 6.2) will be descriptively summarized.

Protocol amendment 02 has updated the total study duration to 2 years. Babies or infants that have passed the 2-year assessments after the amendment implementation are not required to continue further within the study, nor do they need to complete any subsequent study-related assessments.

Descriptive summaries will utilize data collected up to and including the 2-year assessments. Data collected beyond the 2 year assessment will be presented, but not included in the summaries.

No type I error adjustments are planned.

## **3. PLANNED ANALYSES**

All planned analyses will be done using SAS version 9.3 or higher. The Analysis Data Model (ADaM) will be created per ADaM implementation guide version 1.1. Details on derivation of variables will be specified in the specification document of ADaM. All analysis tables, listings, and figures will be generated based on ADaM and/or Study Data Tabulation Model (SDTM).

### **3.1. Interim Analyses**

There is no formal interim analysis planned for this study.

### **3.2. Final Analyses**

The final planned analyses will be performed after the completion of the following sequential steps:

1. All subjects have completed the study as defined in the protocol.
2. All required database cleaning activities have been completed and the final database release and database freeze has been declared by Data Management.
3. All criteria for unblinding the study have been met.
4. Actual treatment data have been distributed.

